5.1.4 Follow-up

5.1.4.1 Safety Follow-up Period

Upon completion of study therapy (or up to a maximum of 96 weeks, if applicable), or once the participant has received the last administration of any study treatment (ie, at EOT), all participants will enter a safety follow-up period.

For participants who complete all scheduled cycles of therapy, the EOT visit will be the same visit as the last scheduled and completed on-treatment visit and will be the start of the safety follow-up period. For participants who do not complete all scheduled cycles of therapy, the EOT visit will be the most recent on-treatment visit (with all available safety and response data) and will not need to be repeated. Accordingly, for these participants, this visit will be considered the start of the safety follow-up period.

After the EOT visit, all participants will be evaluated for any new AEs for at least 100 days after the last dose of study treatment.

All participants will be required to complete the 3 clinical safety follow-up visits, regardless of whether new anti-cancer therapy is started, except those participants who withdraw consent for study participation.

5.1.4.2 Survival Follow-up

In parallel with the safety follow-up period, all participants will continue on the survival follow-up period. Participants will be followed up for survival at each Safety Follow-up visit and then by telephone

The duration of this follow-up is up to following the last dose of study treatment, although a longer follow-up period could be considered in selected cases if an efficacy signal is apparent. Tumor assessment scans, for participants who have ongoing clinical benefit beyond the period following the end of treatment, may continue to be collected as part of standard-of-care treatment upon agreement between the Sponsor and Investigator. Subsequent therapies will also be recorded in this survival follow-up period.

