	observation period then BMS-986258, over approximately . BMS-986258	infusion
	will begin at least after completion of the infusion of nivolumab. BMS	
	infusions will require a observation period following the completion of the	infusion
	for the first 2 doses for each participant. Shorter infusion times for BMS-986258 may	be used
	for initial dose panels and longer infusion times	will be
	used for the higher dose panels.	
	. Please refer to the Pharmacy Manual for dose-specific infusion time	mes and
	administration details for nivolumab and BMS-986258.	

 Tumor progression and response endpoints will be assessed using RECIST v1.1 criteria for solid tumors.

Follow-up:

- Safety Follow-up Period:
 - Upon completion of study therapy (or up to a maximum of 96 weeks, if applicable), or once the participant has received the last administration of any study treatment (ie, at end of treatment), all participants will enter a safety follow-up period for 100 days.
 - For participants who complete all scheduled cycles of therapy, the end of treatment (EOT) visit will be the same visit as the last scheduled and completed on-treatment visit and will be the start of the safety follow-up period. For participants who do not complete all scheduled cycles of therapy, the EOT visit will be the most recent on-treatment visit (with all available safety and response data) and will not need to be repeated. Accordingly, for these participants, this visit will be considered the start of the safety follow-up period.
- Survival Follow-up Period:
 - In parallel with the safety follow-up period, all participants will continue on the survival follow-up period. Participants will be followed up for survival at each Safety Follow-up

Protocol Amendment No.: 07

visit and then by telephone , loss to follow-up, withdrawal of consent, or conclusion of the study, whichever comes first. Subsequent therapies will also be recorded in this survival follow-up period.

Protocol Amendment No.: 07

[figure not shown]
Protocol Amendment No.: 07

Date: 16-Jun-2021

Date: 16-Jun-2021

[figure not shown]

Date: 16-Jun-2021

Approved v2.0

930120074 9.0

Protocol Amendment No.: 07 Date: 16-Jun-2021

[figure not shown]
Approved v2.0 930120074 9.0

CA031002

Date: 16-Jun-2021

Date: 16-Jun-2021

Clinical Protocol
BMS-986258

CA031002
Anti-TIM-3 mAb

Protocol Amendment No.: 07

Date: 16-Jun-2021

[figure not shown]

30

Protocol Amendment No.: 07

[figure not shown]

Date: 16-Jun-2021

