5.1.3 Treatment Period

The dosing regimen of BMS-986258 is Q4W.

Refer to Section 5.1 and

All participants will be treated for up to 96 weeks. The treatment period will consist of up to 12 treatment cycles (each cycle is 8 weeks in length). Following each treatment cycle, the decision to treat a participant with additional cycles of study therapy (up to a maximum of 12 cycles) will be based on response assessment at the end of each cycle. Continuous safety evaluation and tumor assessment (every 8 weeks [Q8W]) will guide the decision to treat a participant with additional cycles of study therapy if the participant has confirmed clinical benefit (up to a maximum of 96 weeks) for all study parts.

Study visits will be performed every 2 weeks for the first 8 weeks following the first dose of study treatment for the BMS-986258 Monotherapy Escalation (Part A), BMS-986258 with rHuPH20 SC for first dose (Part A1), and BMS-986258 in Combination with Nivolumab (Part B). Study visits at Cycle 2 and beyond will be every 4 weeks. During Cycles 1 and 3 of the treatment period, additional study visits to collect samples for intensive PK, ADA, required. See Section 9.5 for further details. In Part C (BMS-986258 in

Combination with nivolumab Cohort Expansion), study visits will be performed every 2 weeks for the first cycle. Study visits at Cycle 2 and beyond will be every 4 weeks.

In Part A (BMS-986258 Monotherapy Escalation), BMS-986258 will be administered Q4W. BMS-986258 will be infused according to dosing and infusion times in Table 7.1-1. Shorter infusion times may be used for initial dose panels and longer infusion times will be used for the higher dose panels.

In Part A1 (BMS-986258 SC for first dose), BMS-986258 will be co-administered with rHuPH20 for the first dose of BMS-986258 in Cycle 1. All subsequent doses will be administered as monotherapy IV Q4W. Alternatively, participants in cohort A1 who have received SC BMS-986258 on Cycle 1 Day 1 will be offered the option to receive subsequent IV combination therapy of BMS-986258 with nivolumab (480 mg) at the highest dose of BMS-986258 that has been shown to be safe and tolerable in the dose escalation (Part B). Treatment will be given Q4W twice per cycle, for up to twelve 8-week cycles (96 weeks).

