8.1.5 Post-Study Treatment Follow-up

In this study, safety and efficacy are key endpoints of the study. Post-study follow-up is of critical importance and is essential to preserving participant safety and the integrity of the study. Participants who discontinue study treatment must continue to be followed (in this study or a rollover study) for collection of outcome and/or survival follow-up data as required and in line with Section 5 and until death or the conclusion of the study.

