10.3.7 Other Analyses

Other exploratory analyses will be described in detail in the Statistical Analysis Plan finalized before database lock. Summary of OS rate will be analyzed similarly to PFS rate.

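### Survival follow-up is counted from the last dose, so Kaplan-Meier OS rates later than that follow-up period, measured from first dose, can be biased upward; Section 8.1.5 words the end of follow-up differently

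*Combined protocol and SAP*

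**What the plan says.** Section 5.1.4.2 runs survival follow-up for a limited time from the last dose (the length is redacted), "although a longer follow-up period could be considered in selected cases if an efficacy signal is apparent". It does not say what counts as a selected case or an efficacy signal, who decides, when, or whether the decision applies to a participant or a cohort. The next sentence deals with imaging and is worded for individuals: "Tumor assessment scans, for participants who have ongoing clinical benefit beyond the period following the end of treatment, may continue to be collected".

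The end of follow-up is described in two other places. Section 8.1.5 requires participants who discontinue treatment to be followed "in line with Section 5 and until death or the conclusion of the study". The synopsis gives a list that ends "loss to follow-up, withdrawal of consent, or conclusion of the study, whichever comes first"; the text just before it is missing from the public copy.

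On exposure, Section 5.1.3 says "All participants will be treated for up to 96 weeks", and Section 8.1 stops treatment at documented progression unless the criteria for treatment beyond progression are met.

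On analysis, Section 10.3.7 says "Summary of OS rate will be analyzed similarly to PFS rate". Section 10.3.1 estimates PFS rates at 6, 9 and 12 months by Kaplan-Meier and leaves the censoring scheme for DOR, PFS and OS rate to a later SAP. No OS time point is visible.

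**The concern.** The clock for ending survival follow-up starts at the last dose, while OS is measured from the start of treatment. A participant who stops after one or two doses because of progression can leave follow-up X months later. One who stays on treatment for 96 weeks is followed for about 22 months longer. The date on which a living participant is censored therefore tracks how well that participant did.

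Kaplan-Meier handles censoring by letting those still under observation stand in for those who have left. Beyond X, those still under observation are increasingly the ones who stayed on treatment, and their better survival is credited to everyone. An SAP can choose how to censor, but it cannot recover survival status that was never collected.

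The differing wording matters in practice as well. For someone who enrols early and progresses quickly, last dose plus X and the conclusion of a study of approximately 4 years (Section 5.1) may be far apart, and a site cannot tell which of them ends the telephone contacts.

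**Working it through.** The plan states no OS rate, event count or precision for this point, so there is no figure to reproduce. The check asks when a bias arises, in which direction, how large it is, and which rule causes it.

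**Inputs from the protocol.** Maximum treatment is 96 weeks, or 96 × 7 / 30.44 = 22.1 months. Dosing is every 4 weeks and normally stops at progression. Follow-up ends at last dose + X, with X redacted. The method is Kaplan-Meier.

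**Step 1: where bias can arise.** The last dose cannot precede the first, so every living, contactable participant is due at least X months of follow-up from first dose. Nobody is censored by the cap before X, and the bias at any time up to X is zero.

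**Step 2: a hand check beyond X.** Assume 20% long-benefit participants (median OS 30 months, treated 22 months) and 80% others (median OS 9 months, treated exactly 3 months), with exponential survival and no extension.

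- True OS at 24 months: 0.8 × 2^(−24/9) + 0.2 × 2^(−24/30) = 0.126 + 0.115 = 0.241.
- The 80% group is censored at 3 + X. From then to month 24 only the long-benefit group is at risk, so the Kaplan-Meier value is S(3 + X) × 2^(−(24 − 3 − X)/30).
- X = 12: S(15) = 0.8 × 0.315 + 0.2 × 0.707 = 0.393; × 2^(−9/30) = 0.812 gives 0.320, a bias of +7.9 points.
- X = 6: S(9) = 0.8 × 0.500 + 0.2 × 0.812 = 0.562; × 2^(−15/30) = 0.707 gives 0.398, a bias of +15.7 points.
- X = 24: first censoring is at month 27, so the bias at month 24 is zero.

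Fixing treatment at 3 months exaggerates the effect somewhat. Letting it vary around a mean of 3 months (simulation, 400,000 participants) gives 30.4% for X = 12 and 37.0% for X = 6, against a true 24.0%. Both figures are the same with or without extending the long-benefit group.

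**Step 3: a fuller model.** Assumptions, none from the documents: response rate 10% or 20%; median PFS 2.5 or 3.5 months in non-responders and 14 months in responders; median survival after progression 6 or 9 months in non-responders and 9 or 12 months in responders; dosing every 4 weeks to progression or 96 weeks. Extension went to nobody, to responders, to half of responders, or to those treated for at least 6 months. Ranges cover these scenarios (400,000 participants each).

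| X (months) | Bias at month 12 (points) | Bias at month 24 (points) | Bias at month 36 (points) |
|---|---|---|---|
| 6 | +4.4 to +6.4 | +8.5 to +20.4 | see Step 4 |
| 12 | 0 | +3.9 to +6.6 | +3.9 to +8.2, where estimable |
| 24 | 0 | 0 | +1.3 to +1.9 |
| 36 | 0 | 0 | 0 |

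**Step 4: which rule causes it.** With X = 6 and a 20% response rate, the month-24 bias is +20.4 points with no extension, +15.9 with all responders extended, and +11.4 with those treated at least 6 months extended. The cap alone produces the bias, and extending selected participants usually reduces it at a given time point. What the extension adds is that rates later than about 22 months + X become estimable at all, from selected participants only. In the same setting, OS at month 36 cannot be estimated without extension and reads 14.2 points too high with responders extended.

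**Step 5: the remedy.** With everyone followed to a common study end (assumed 48-month study, 24-month accrual), or with the whole cohort extended to 48 months, the bias is 0.0 at every time point from 6 to 36 months.

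**The case against.** The strongest reply is that nothing visible shows a biased rate will ever be reported. X is redacted, which is not a fault of the plan, and the only visible time points are the PFS ones. If OS is summarised at 6, 9 and 12 months and X is at least 12 months, the bias is exactly zero. That stands, and it makes the finding conditional.

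A reader might infer more, in three ways:

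- **That the efficacy-triggered extension inflates OS.** Step 4 shows otherwise: the cap is the main cause. The text is also open to a cohort-level reading, since individuals are covered separately in the sentence on scans. An extension of whole cohorts would cause no selection within a cohort.
- **That inflated OS would undermine a historical comparison.** The historical benchmark in Section 10.1.2 is for response rate. No historical OS comparison is stated, and OS is not among the visible primary or secondary endpoints.
- **That Section 8.1.5 flatly contradicts Section 5.1.4.2.** The same sentence in 8.1.5 defers to Section 5, and the synopsis list is partly missing. The two still name different ends, and the deference does not tell a site which one applies.

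It can also be said that censoring belongs in the SAP. That is right for a reporting limit, but not for data collection.

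**Conclusion.** The point holds in conditional form. Because follow-up ends at last dose + X and last dose depends on progression, Kaplan-Meier OS rates at times later than X from first dose can be biased upward; rates up to X are not. At 24 months the size is about +4 to +7 points for X = 12 months, about +8 to +20 for X = 6 months, and zero for X of 24 months or more. These figures rest on assumed response rates, PFS and post-progression survival, and on an unknown X. The documents do not support saying that the planned OS rates are biased, because neither X nor any OS time point is visible. The impact is confined to late OS estimates in an other analysis. Separately, Section 5.1.4.2, Section 8.1.5 and the synopsis should be reconciled on when survival follow-up ends.

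**What to change.** 1. State one end of survival follow-up in Section 5.1.4.2, Section 8.1.5 and the synopsis: death, withdrawal of consent, loss to follow-up or conclusion of the study, with a common cut-off date for all participants in a cohort.
2. In Section 5.1.4.2, say that any extension, once triggered, applies to every living, consenting participant in that cohort regardless of response.
3. If the cap from last dose is kept, name the OS time points in the SAP and report Kaplan-Meier OS rates only up to X months from first dose.

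Items 1 and 2 cost protocol wording and some additional telephone contacts of a kind already planned, with no new visits or procedures. Item 3 costs nothing in conduct but gives up late OS rates.

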5.1.5 Data Monitoring Committee and Other External Committees

BMS has in place a multi-layered process for ensuring patient safety through close collaboration of study site investigators, the BMS study team, and the BMS Global Pharmacovigilance and Epidemiology (GPVE)-led Medical Surveillance Team (MST). This collaborative process constitutes the Data Safety Monitoring Plan for the study as detailed below:

Study safety is evaluated continuously by representatives of BMS GPVE, who operate independently from the clinical team and monitor safety across all BMS protocols. AEs are monitored continuously by GPVE. Signal detection is performed at least monthly and ad hoc throughout the study by the MST composed, at a minimum, of the GPVE medical safety assessment physician (Chairman of the MST) and GPVE single case review physician, the study medical monitor(s), the study biostatistician, and epidemiologist. The MST monitors actual or potential issues related to patient safety that could result in a significant change in the medical benefit/risk balance associated with the use of study drugs. Furthermore, investigators will be kept updated of important safety information, such as DLTs, during teleconferences between investigators and the BMS clinical team that will be held at least every 2 weeks during dose escalation and at least monthly during cohort expansion. If appropriate, select safety issues may be escalated to a senior level, multidisciplinary, BMS-wide Medical Review Group for further evaluation and action.

To support safety oversight, BMS has established ongoing processes for collection, review, analysis, and submission of individual AE reports and their aggregate analyses. Because this is an open-label study, the BMS medical monitor and the investigators will have access to all data necessary for safety evaluation.

All participants in this study represent individuals with high unmet medical need, as the prognosis for advanced/metastatic solid tumors is generally very poor.

BMS has elected not to use a Data Monitoring Committee for this study. In addition to the comprehensive safety-monitoring plan outlined above, the following key points were considered for this decision:

• This is an open-label study.

The eligibility criteria exclude participants with disease characteristics that could predispose to higher risk of morbidity.

- Exclusion of participants with known autoimmunity also applies as they could be at risk for exacerbation of their condition by the administration of therapies that relieve immune suppression such as BMS-986258 and nivolumab.
- Participants will be observed frequently for clinical evaluation and blood counts during dose escalation.
- Well-defined discontinuation criteria are established in the protocol for individual participants for both safety and treatment futility with clear criteria for treatment discontinuation, dose delay, and toxicity management.
- For the combination therapy with nivolumab, management algorithms for immune-related events are well established based on the clinical experiences from the over 23,500 subjects who were exposed to nivolumab as either monotherapy or in combination with other agents, in the past as well as in ongoing studies.

5.2 **Number of Participants**

[figure not shown]
The approximate number of participants will be up to as shown below. Part A Monotherapy Escalation: The total sample size is up to approximately including to assess the MTD/MAAD and an additional in NSCLC PD cohorts. Part A1: SC Dose: The total sample size is up to approximately participants to evaluate up to dose levels. Part B Combination Escalation: The total sample size is up to approximately participants, participants to assess the MTD/MAAD in combination and in NSCLC PD including cohorts.

Part C Cohort Expansion: Approximately up to participants will be treated in each of the 5 tumor cohorts (up to a total of across tumors).

5.3 **End of Study Definition**

The start of the study is defined as the first visit for the first participant screened. Similarly, the end of the study is defined as the last visit or scheduled procedure shown in the Schedule of) for the last participant. Primary study completion is defined as the final date on which data for the primary endpoint are expected to be collected, if this is not the same.

5.4 Scientific Rationale for Study Design

cells, therefore it is expected that TIM-3 blockade will promote T-cell activation, proliferation,

Protocol Amendment No.: 07

Date: 16-Jun-2021 58

[figure not shown]
effector function, and survival. TIM-3 expression in tumor samples will be assessed retrospectively in this study.

The study design includes the following:

- Pre-Screening for only)
 (Part A and B NSCLC PD cohorts only)
- Screening period
- Treatment period of up to twelve 8-week cycles, totaling 96 weeks
- Dose escalation phases in monotherapy and combination with nivolumab
- Cohort expansion phase
- Safety follow-up period of 100 days
- Survival follow-up period of

The rationale for the individual elements of the study design is given below.

5.4.1 Rationale for the Monotherapy Dose Escalation (Part A)

BMS-986258 has never been tested in humans; however, the experiments described above suggest a role for BMS-986258 as monotherapy in advanced solid tumors. This study will evaluate the safety profile, tolerability, preliminary efficacy, PK, and PD of IV doses of BMS-986258 administered Q4W, and in combination with nivolumab (Q4W) in participants with select advanced solid tumors. Part A will provide data for BMS-986258 as monotherapy that may be used in future studies in association with drugs other than nivolumab.

5.4.2 Rationale for Subcutaneous Administration of BMS-986258 (Part A1)

rHuPH20 is a recombinant form of hyaluronidase, a human enzyme that degrades hyaluronan, an extracellular matrix component that poses a barrier to large injection volume and fluid flow at the SC injection site, therefore, decreasing the viscosity of SC extracellular matrix, and enabling a rapid delivery of large volume of study drug. It improves the SC absorption rate, thus it has the potential to improve bioavailability.

Protocol Amendment No.: 07

rHuPH20 has dose-dependent, usually local, mild, transient and reversible side effects. rHuPH20 has a local half-life < 30 minutes and systemic half-life < 5 minutes. Additional details are provided in version 08 of the rHuPH20 IB. 38

Part A1 will be conducted to obtain preliminary data on the PK profile of BMS-986258 when administered SC combined with rHuPH20 in comparison to IV administered BMS-986258. This SC cohort will initiate after IV dose(s) and schedule(s) have been shown to be safe in Part A.

SC administration has the potential to reduce infusion time and provide greater convenience and comfort for oncology patients. Co-administration of rHuPH20 (a tissue permeability enhancer) may further enable to overcome barriers of SC drug delivery especially for large mAbs with regards to time and volume to be administered. As of 15-Nov-2019, rHuPH20 has been administered to 1592 participants in 30 clinical studies conducted under the US rHuPH20 IND. In these studies, individual doses have ranged from 15 to 96,000 U rHuPH20. Across all studies, SC injections of rHuPH20 were generally well tolerated in healthy subjects, dehydrated pediatric subjects, hospice and palliative care subjects, subjects with type 1 and 2 diabetes, and subjects with RA. Subcutaneous injections of rHuPH20 alone or in combination with lactated Ringer's, normal saline, co-injected drugs (morphine, ceftriaxone, insulin, and insulin analogs), or biologic products (IgG and adalimumab) have been well tolerated in all clinical trials. Adverse events were generally mild, transient injection site reactions, including erythema, pain, bruising, pruritus, burning, tenderness, edema, induration, irritation, paresthesia, numbness, and rash. Moderate injection site reactions, which have occurred less frequently, include burning, erythema, pain, and numbness. Mild-to-moderate headache was also commonly reported. Adverse events in these trials have otherwise generally reflected the adverse reaction profiles of the co-administered drug or have been associated with the rapid introduction of a relatively large volume of fluid in the SC space.

A large safety database exists for approved products coformulated with rHuPH20 SC is available, including Herceptin®SC, HYQVIA®, and RITUXAN HYCELA™/MabThera® SC/Rituxan®.³⁹ Public data presented to the FDA to support coadministration of rituximab (1400 mg and 1600 mg) and rHuPH20, summarizing data from randomized PK bridging trials in patients with follicular lymphoma, CLL, or DLBCL (SparkThera, SABRINA, SAWYER, MabEase, PrefMab) show: (1) comparable Ctrough and overall exposure; (2) comparable safety, aside from administration site reactions; and (3) comparable efficacy (ORR, CRR, PFS, EFS, and OS in various studies) for SC versus IV routes. Injection site reactions (discomfort, erythema) were increased following SC administration, occurring in 1.9% - 25.9% of subjects; these were generally mild and did not limit therapy. Importantly, patient preference and patient-reported outcomes were evaluated in a randomized crossover trial (PrefMab) of 743 previously untreated patients with DLBCL or FL receiving R-CHOP, R-CVP, or R-Bendamustine to SC versus IV administration. Over 80% of patients preferred SC administration, due to reduced time for administration and greater comfort.⁴⁰

Studies have shown that the BA of mAbs following SC administration approximates 70% (50% to 80%), with lower Cmax and a delayed time of maximum observed concentration (Tmax) compared

Protocol Amendment No.: 07

to IV. The doses evaluated in these studies ranged from 2 to 1400 mg administered with or without rHuPH20. 38,41,42,43 Drugs administered with rHuPH20 provide an added advantage of faster Tmax as compared to when administered without rHuPh20. The PK of BMS-986258 is expected to follow a similar profile as other IgG mAbs and hence the BA is expected to be approximately 70% in the dose range planned in Part A when administered SC.

Overall, these data suggest that SC administration of BMS-986258 with rHuPH20, at a dose previously shown to be safe intravenously, should be feasible and tolerable.

For each participant in Part A1, 1200 mg of BMS-986258 will be co-administered with rHuPH20 SC for the first dose in Cycle 1. All subsequent doses of BMS-986258 will be administered as monotherapy 1200 mg IV, Q4W twice per cycle, for up to twelve 8-week cycles (96 weeks). Alternatively, participants in cohort A1 who have received SC BMS-986258 on Cycle 1 Day 1 will be offered the option to receive subsequent IV combination therapy of BMS-986258 with nivolumab (480 mg) at the highest dose of BMS-986258 that has been shown to be safe and tolerable in the dose escalation (Part B). Treatment will be given O4W twice per cycle, for up to twelve 8-week cycles (96 weeks). The dose selected for Part A1 is based on the safety and tolerability observed in Part A. Based on the expected bioavailability of for SC administered mAbs, the 1200 mg SC dose is expected to produce exposures similar to IV 800 mg Q4W, which has been found to be within the range of linear PK. Dose-dependent increases in soluble TIM-3 were observed in Part A, and preliminary data suggest that target engagement is suboptimal at doses below 800 mg IV Q4W. Thus, given the totality of safety and PK and biomarker characteristics of BMS-986258 IV, 1200 mg SC Q4W is considered as potentially therapeutic, and therefore was chosen as starting dose in Part A1. Additional cohorts at higher doses may be tested depending on the safety and PK data of the dose at 1200 mg level.

